6.5.2 Prohibited concomitant therapy

Other investigational and antineoplastic therapies

Other investigational therapies must not be used while the patient is on the study. Anticancer therapy (chemotherapy, biologic or radiation therapy (that includes > 30% of the bone marrow reserve), and surgery) other than the study treatment must not be given to patients while the patient is on the study medication. If such agents are required for a patient then the patient must be discontinued from the study.

CYP inhibitors

Strong inhibitors of CYP3A4, as listed below, are prohibited because BGJ398 (infigratinib) is a likely substrate of this isoenzyme. Caution should be used during administration of moderate inhibitors. Please note that the list may not be comprehensive. In addition, the following food products are prohibited: Seville oranges or juice, grapefruit, grapefruit juice, grapefruit hybrids, pomegranates, and pomelos.

- a. Anti-fungal agents: Ketoconazole, itraconazole, fluconazole
- b. Anti-retroviral agents: Ritonavir, nelfinavir, indinavir, saquinavir, amprenavir,
- c. atazanavir, fosamprenavir
- d. Anti-biotic agents: Clarithromycin, telithromycin, erythromycin
- e. Others: Aprepitant, diltiazem, verapamil, nefazodone, grapefruit juice

Patient on strong or moderate CYP3A4 inducers or inhibitors or medications that rely on CYP3A4 for metabolism, should switch whenever possible to a product with less interaction with/reliance on the pathway or patient should be on a stable dose of the medication prior to enrollment.

CYP inducers

Strong inducers of CYP3A4 are prohibited because their usage would likely decrease the exposure of BGJ398 (infigratinib). Caution should be used during administration of moderate inhibitors.

Phosphorus and calcium

Medications that increase the serum levels of phosphorus and/or calcium are prohibited. Medications include, but are not limited to, calcium, phosphate, vitamin D, parathyroid hormone (PTH).

Herbal medications

Herbal preparations/medications are not allowed throughout the study. These herbal medications include, but are not limited to: St. John's wort, Kava, ephedra (ma huang), ginkgo biloba, dehydroepiandrosterone (DHEA), yohimbe, saw palmetto, and ginseng. Patients should stop using these herbal medications 7 days prior to first dose of study drug.

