 - Wide field radiotherapy (including radioisotopes) ≤ 2 weeks prior to starting study drug unless there are ongoing side effects $>$ Grade 2.

9. Patients who are currently receiving treatment with agents that are known strong inducers or inhibitors of CYP3A4 are prohibited.
10. Enzyme inducing anti-epileptic drugs.
11. Consumption of grapefruit, grapefruit juice, pomegranates, star fruits, Seville oranges or products within 7 days prior to first dose.
12. Use of medications that are known to prolong the QT interval and/or are associated with a risk of Torsades de Pointes 7 days prior to first dose.
13. Use of amiodarone within 90 days prior to first dose.
14. Use of medications that increase serum levels of phosphorus and/or calcium.
15. Current use of therapeutic doses of warfarin sodium or any other coumadin-derivative anticoagulants. Heparin and/or low molecular weight heparins or other anticoagulants are allowed.
16. Insufficient bone marrow function
 - ANC $< 1,000/\text{mm}^3$ [$1.0 \times 10^9/\text{L}$]
 - Platelets $< 75,000/\text{mm}^3$ [$75 \times 10^9/\text{L}$]
 - Hemoglobin $< 10.0 \text{ g/dL}$
17. Insufficient hepatic and renal function
 - Total bilirubin $> 1.5 \times \text{ULN}$ (unless evidence of Gilbert's disease)
 - AST/SGOT and ALT/SGPT $> 2.5 \times \text{ULN}$
 - Serum creatinine $\geq \text{ULN}$ and/or calculated or measured creatinine clearance $< 75\% \text{ LLN}$
18. Calcium-phosphate homeostasis
 - Inorganic phosphorus outside of normal limits
 - Total and ionized serum calcium outside of normal limits
19. Clinically significant cardiac disease including any of the following:
 - Congestive heart failure requiring treatment (NYHA grade ≥ 2), LVEF $< 50\%$ as determined by MUGA scan or ECHO, or uncontrolled hypertension (refer to WHO-ISH guidelines)
 - History or presence of clinically significant ventricular arrhythmias, atrial fibrillation, resting bradycardia, or conduction abnormality
 - Unstable angina pectoris or acute myocardial infarction ≤ 3 months prior to starting study drug
 - QTcF $> 450 \text{ msec}$ (both genders)
 - History of congenital long QT syndrome
20. Pregnant or nursing (lactating) women, where pregnancy is defined as the state of a female after conception and until the termination of gestation, confirmed by a positive hCG laboratory test
21. Known positive serology for HIV, active Hepatitis B, and/or active Hepatitis C infection.

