- Patients on strong or moderate CYP3A4 inducers or inhibitors or medications that rely on CYP3A4 for metabolism, should switch whenever possible to a product with less interaction with/reliance on the pathway or patient should be on a stable dose of the medication prior to enrollment

6.1.3 Ancillary treatments with anti-emetics, phosphate lowering agents, anti-diarrheals, and growth factors

Anti-emetics

Anti-emetics are allowed for the treatment of nausea or vomiting. It is recommended to avoid using drugs that are known to cause QT prolongation. Note that some anti-emetics have a known risk for Torsade de Pointes, and therefore need to be used with caution. Aprepitant is both a sensitive substrate and a moderate CYP3A4 inhibitor and can be used with caution if an alternative is not available.

Phosphate-lowering therapy

Phosphate-lowering treatment, including low phosphate diet and phosphate binding therapy, such as sevelamer hydrochloride, should be implemented prophylactically at study drug initiation and modified as clinically indicated throughout BGJ398 (infigratinib) administration

Anti-diarrheals

No prophylactic anti-diarrhea therapy is recommended. However, patients should have loperamide tablets at home in case BGJ398 (infigratinib) induced diarrhea occurs and should call the study doctor or study staff at the first onset of loose stools. Patients should also be instructed to record the number of stools and report severe symptoms (e.g., fever or dizziness on standing). Initial management of mild to moderate diarrhea should include dietary modifications (e.g., eliminating all lactose-containing products and high-osmolar dietary supplements), extra fluids to prevent dehydration and loperamide at an initial dose of 4mg followed by 2 mg every 4 hours or after every unformed stool but not to exceed 16 mg/day.

In case of persistent, (i.e. >48 hrs on loperamide), or aggravated diarrhea, the patient should be seen at the investigational site or in the physician's office/outpatient center for further evaluation, including complete stool and blood work-up and intensified anti-diarrhea treatment per institutional guidelines.

Hematopoietic growth factors

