6.1.5 Dose modification and dose delay

For patients who do not tolerate the protocol-specified dosing schedule, dose adjustments are permitted in order to allow the patient to continue the study treatment. The following guidelines need to be applied:

These changes must be recorded appropriately.

All dose modifications should be based on the worst preceding toxicity.

Following resolution of toxicity to baseline or \leq grade 1, treatment is resumed at either the same or lower doses of study drugs as per the criteria in [Table 6-3](#). If treatment is resumed at the same doses of study drugs, and the same toxicity recurs with the same or worse severity regardless of duration, doses must be reduced to the next lower dose level. If treatment is resumed at the lower doses of study drugs, and the same toxicity recurs with the same or worse severity, the patient must discontinue study treatment.

If a patient requires a dose delay of > 14 consecutive days of BGJ398 (infigratinib) from the intended day of the next scheduled dose, then the patient should be discontinued from the study treatment, unless extenuating circumstance occur and approval from Novartis is obtained.

Patients who discontinue the study for a study related adverse event or an abnormal laboratory value must be followed as described in [Section 6.1.5](#).

Table 6-2 Dose reduction table

Dose reduction			
	Starting dose level 0	Dose level - 1	Dose level - 2
BJG398	125 mg	100 mg	75 mg

A third or subsequent reduction (to 50 mg) in dose may be allowed if the patient is clearly benefiting from study treatment (i.e., stable disease, partial response, or complete response) but is experiencing adverse events that prevent continued treatment at the already reduced dose.

Table 6-3 Recommended dose modifications for BGJ398 (infigratinib) treatment

6.2 Worst Toxicity CTCAE v4.03 Grade (unless otherwise specified)	6.3 Recommended Dose Modifications any time during a cycle of therapy
Cardiac disorders	
Cardiac - Prolonged QTcF interval	

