Grade 1 and 2 : QTcF \geq 481msec and \leq 500 msec (asymptomatic)	
Maintain dose level of BGJ398 (infigratinib) ECG assessments should be performed for 2 additional cycles at the same frequency as in cycle 1, or as clinically indicated
 
 If ECG assessments show no QTcF \geq 481 msec, for subsequent cycles ECG monitoring will be performed as per visit schedule. If ECG assessments are still abnormal (QTcF \geq 481 msec and \leq500 msec), then ECG monitoring must continue at the same frequency as in cycle 1 for all subsequent cycles.
Grade 3 : QTcF > 500msec as identified on the ECG by the investigator	
 Hold BGJ398 (infigratinib). Monitor patient with hourly ECGs until the QTcF has returned to baseline. Perform further monitoring as clinically indicated. Exclude other causes of QTcF prolongation such as hypokalemia, hypomagnesaemia and decreased blood oxygenation. Patients should receive appropriate electrolyte replacement and should not receive further BGJ398 (infigratinib) until electrolytes are documented to be within normal limits. 
Once the QTcF prolongation has resolved and if the QTcF prolongation was confirmed by the central reader, patients may be re-treated at one lower dose level at the investigator's discretion
 
 ECG assessments should be performed for 2 additional cycles at the same frequency as in cycle 1 or as clinically indicated

6.2 Worst Toxicity CTCAE v4.03 Grade (unless otherwise specified)	6.3 Recommended Dose Modifications any time during a cycle of therapy
	
 ○ If ECG assessments show no QTcF \geq 481 msec, for subsequent cycles ECG monitoring will be performed as per visit schedule. ○ If ECG assessments are still abnormal (QTcF \geq 481 msec and \leq500 msec), then ECG monitoring must continue at the same frequency as in cycle 1 or as clinically indicated, for all subsequent cycles ● Patients who experience recurrent QTcF \geq 500msec after one dose reduction will be discontinued from study. 
NB: If ventricular arrhythmia or Torsades de Pointes is observed in a patient, he/she will be discontinued from the study.

Cardiac disorders - others Grade \geq 3, or congestive heart failure \geq 2	Discontinue patient from study treatment.
Investigations-Hematology	

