
Serum creatinine
 
Grade 1 and Pi >5.5 mg/dL and/or tCa x Pi >55 mg²/dl² and despite phosphorus lowering therapy for at least 14 days
 
Grade 2 (> 1.5 - 3.0 x ULN)
 
Grade 2 and Pi >5.5 mg/dL and/or tCa x Pi >55 mg²/dl² and despite phosphorus lowering therapy for at least 14 days
 
Grade ≥ 3 (> 3.0 x ULN)
	
Hold dose of BGJ398 (infigratinib) until resolved to CTCAE Grade ≤ 1 or baseline
 
 • If resolved in ≤ 7 days, maintain dose level of BGJ398 (infigratinib). • If resolved in > 7 days, ↓ 1 dose level of BGJ398 (infigratinib). 
Hold dose of BGJ398 (infigratinib) until resolved to CTCAE Grade ≤ 1 or baseline
 
 • If resolved in ≤ 7 days, maintain dose level of BGJ398 (infigratinib). • If resolved in > 7 days, ↓ 1 dose level of BGJ398 (infigratinib). 
Discontinue patient from study treatment
 
Discontinue patient from study treatment.

Investigations – Hepatic	

Blood bilirubin (patients with Gilbert Syndrome these dose modifications apply to changes in direct bilirubin only)
 
Grade 2 (>1.5 – 3.0 x ULN)
 
Grade ≥ 3 (> 3.0 x ULN)
	
Hold dose of BGJ398 (infigratinib) until resolved to CTCAE Grade ≤ 1
 
 • If resolved in ≤ 7 days, maintain dose level of BGJ398 (infigratinib). • If resolved in > 7 days, ↓ 1 dose level of BGJ398 (infigratinib). 
Discontinue patient from study treatment.

6.2 Worst Toxicity CTCAE v4.03 Grade (unless otherwise specified)	6.3 Recommended Dose Modifications any time during a cycle of therapy
	Note: If CTCAE Grade 3 or 4 hyperbilirubinemia is due to hemolysis, then ↓ 1 dose level of BGJ398 (infigratinib) and continue treatment at the discretion of the Investigator.

AST or ALT Grade 3 (> 5.0 - 20.0 x ULN) without bilirubin elevation > 2.0 x ULN
 
Grade 4 (> 20.0 x ULN) without bilirubin elevation > 2.0 x ULN
	
Hold dose of BGJ398 (infigratinib) until resolved to CTCAE Grade ≤ 1 or baseline
 
 • If resolved in ≤ 7 days, maintain dose level of BGJ398 (infigratinib). • If resolved in > 7 days, ↓ 1 dose level of BGJ398 (infigratinib). 
Discontinue patient from study treatment.

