6.2 Worst Toxicity CTCAE v4.03 Grade (unless otherwise specified)	6.3 Recommended Dose Modifications any time during a cycle of therapy
≥ grade 1 retinal vein occlusion, grade 4 CSR and CSR-like events, and grade 4 other eye disorders	Discontinue BGJ398 (infigratinib)
Other ocular/visual toxicity ≥ grade 3	Hold BGJ398 (infigratinib) until resolution to ≤ grade 1 If resolution in ≤14 days, ↓ 1 dose level, otherwise discontinue BGJ398 (infigratinib)
General disorders	
Fatigue Grade 3	Hold dose of BGJ398 (infigratinib) until resolved to CTCAE Grade ≤ 1 
 • If resolved in ≤ 7 days, maintain dose level of BGJ398 (infigratinib). • If resolved in > 7 days, discontinue patient from study treatment.
Other clinically significant AEs	
Grade 3	Hold dose of BGJ398 (infigratinib) until resolved to CTCAE Grade ≤ 1, then ↓ 1 dose level of BGJ398 (infigratinib).
Grade 4	Discontinue patient from study treatment.
All dose modifications should be based on the worst preceding toxicity. Once a dose has been reduced it will not be increased at a later time even if there is no toxicity. Patients who require more than two dose reductions of BGJ398 (infigratinib) will be discontinued from study drug treatment. If a patient requires a dose delay of > 14 days from the intended day of the next scheduled dose of BGJ398 (infigratinib) then study treatment must be stopped.	

Table 6-4 Toxicity – Follow-up evaluation

TOXICITY	FOLLOW-UP EVALUATION
Metabolic (hyperphosphatemia)	
Serum phosphorus lowering therapy consisting of dietary phosphate intake restriction and oral phosphate binders should be applied as follows:
 
Calcium-containing phosphate binders are not recommended.
 
Starting Cycle 1 Day 1 (beginning with the midday or evening meal on C1D1):
 
 - Restriction of dietary phosphate intake to 600 - 800 mg/day, if BMI ≥ 21kg/m². - Sevelamer 1 tablet (800mg) per meal; i.e. 3 x 800 mg/day.

TOXICITY	FOLLOW-UP EVALUATION

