6.4 Follow up for dose modifications/treatment interruptions

Patients whose treatment is interrupted or permanently discontinued due to an adverse event or abnormal laboratory value must be followed at least once a week for 4 weeks, and subsequently at 4-week intervals, until resolution or stabilization of the event, whichever comes first. If a patient requires a dose delay of > 14 days from the intended day of the next scheduled dose, then the patient must be discontinued from the study. However, the patient will continue to be followed for toxicity as previously described. All patients will be followed for adverse events and serious adverse events for 30 days following the last dose of BGJ398 (infigratinib).

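### Section 6.5.2 bans phosphorus- and calcium-raising medication with no rescue exception and no end date, so a persistent Grade 3 or symptomatic deficit cannot be replaced while the patient is on infigratinib or in a hold

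*Combined protocol and SAP*

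**What the plan says.** **The ban.** Section 6.5.2 reads "Medications that increase the serum levels of phosphorus and/or calcium are prohibited. Medications include, but are not limited to, calcium, phosphate, vitamin D", and its list goes on to parathyroid hormone. It sets no grade, symptom or rescue exception, no approval route and no period. Exclusion 14 bars the same drugs at entry.

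**Phosphate lowering for everyone.** Under section 6.1.3, diet and binder "should be implemented prophylactically at study drug initiation and modified as clinically indicated throughout BGJ398 (infigratinib) administration". Table 6-4 starts sevelamer at 800 mg with each of three meals on Cycle 1 Day 1, with a restricted-phosphate diet if BMI is at least 21.

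**Normal values at entry.** Exclusion 18 rules out abnormal inorganic phosphorus and "Total and ionized serum calcium outside of normal limits". Only deficits that arise on treatment are therefore at issue.

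**Dose rules.** Table 6-3 has rows for high phosphorus and high calcium and none for low values. A low value falls under the catch-all for other clinically significant adverse events. At Grade 3 this says "Hold dose of BGJ398 (infigratinib) until resolved to CTCAE Grade ≤ 1, then ↓ 1 dose level of BGJ398 (infigratinib"; at Grade 4 treatment is discontinued. Replacement is not mentioned.

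**Limit on a hold.** Section 6.1.5 begins "If a patient requires a dose delay of > 14 consecutive days of BGJ398 (infigratinib) from the intended day of the next scheduled dose" and then stops treatment unless Novartis approves otherwise. The footer of Table 6-3 and section 6.4 repeat the limit without that exception.

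**QTcF row.** For QTcF above 500 msec, Table 6-3 says "Patients should receive appropriate electrolyte replacement and should not receive further BGJ398 (infigratinib) until electrolytes are documented to be within normal limits".

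**The concern.** The protocol lowers phosphate in every patient, so an overshoot into hypophosphatemia is foreseeable, and it was seen at this dose and schedule in an earlier study. If phosphorus stays low after the binder and diet are stopped, the usual next step is short-term replacement, and section 6.5.2 forbids it. The site can wait, hold, reduce or stop infigratinib. It cannot give phosphate, calcium or vitamin D without a protocol deviation. Waiting has its own cost, because a hold of more than 14 days ends study treatment.

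What is at stake is patient safety in a small number of patients, and the possible loss of a patient from treatment over a correctable laboratory value.

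**Working it through.** **1. Does any other text open a route?**

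| Situation | What the protocol allows | Replacement medication? |
|---|---|---|
| Low phosphorus, on infigratinib | Reduce or stop sevelamer and diet (6.1.3); food is not banned; binder normally omitted in the off week (6.1.2) | Barred by 6.5.2 |
| Grade 3, still low | Hold, then reduce one level (Table 6-3 catch-all) | Barred by 6.5.2; catch-all silent |
| Symptomatic Grade 1-2, still low | No hold trigger in the catch-all | Barred by 6.5.2 |
| Grade 4 | Discontinue treatment | Not stated that the ban continues |
| Hold over 14 days | Treatment stops (6.1.5, Table 6-3, 6.4) | Not stated that the ban continues |
| QTcF above 500 msec with low phosphorus or calcium | Replace electrolytes (Table 6-3) | Conflict with 6.5.2; no precedence given |

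The protocol writes approval routes where it wants them: exclusion 7 and the 14-day rule in section 6.1.5 both allow one through Novartis. Section 6.5.2 has none, so a site would reasonably read the ban as absolute during treatment and a hold.

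**2. The document's own rates (section 1.2.1.2.1).** X2204 used 125 mg, 21 days on and 7 off, in 63 patients. Any-grade hypophosphatemia was 27.0%: 17/63 = 27.0%. Grade 3-4 was 6.3%: 4/63 = 6.3%. Both reproduce.

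**3. Bounds from the other two studies.** Each lists Grade 3-4 events seen in at least 5% of patients, and neither lists hypophosphatemia.

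- XUS04 (85 patients, same schedule): nausea is listed at 5%. Since 4/85 = 4.71% rounds to 5% and 5/85 = 5.88% rounds to 6%, nausea was 4/85. An unlisted event is then 0 to 3, assuming ordinary rounding.
- X2101 (208 patients, mixed doses and schedules): 10/208 = 4.81% and 11/208 = 5.29%, so an unlisted event is 0 to 10.

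**4. Expected Grade 3-4 hypophosphatemia in 20 patients.** Expected number = 20p; chance of at least one = 1 − (1 − p)^20.

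| Source | p | Expected in 20 | Chance of at least one |
|---|---|---|---|
| All three, 4 to 17 of 356 | 1.12% to 4.78% | 0.22 to 0.96 | 20% to 62% |
| X2204 + XUS04, 4 to 7 of 148 | 2.70% to 4.73% | 0.54 to 0.95 | 42% to 62% |
| X2204 alone, 4/63 | 6.35% | 1.27 | 73% |
| X2204 exact 95% interval | 1.8% to 15.5% | 0.35 to 3.1 | 30% to 97% |

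The ranges in the first two rows come from unreported counts only and leave out sampling error; the last row shows how wide that is for X2204. Every row counts all Grade 3-4 hypophosphatemia, before any compliant step is taken. The number still low afterwards is smaller, and the documents do not give it. Symptomatic lower-grade cases are not reported either. No hypocalcemia is listed in any of the three studies.

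**The case against.** The strongest defence is that a strict ban suits this drug. Hyperphosphatemia was 82.5% in X2204, with 15.9% at Grade 3-4, and section 1.2.1.1.2 treats ectopic mineralization as an on-target effect. The binder can be stopped, each cycle normally has a week without drug or binder, and Cycle 1 chemistry is drawn on Days 1, 8, 15 and 21. A site facing a real emergency would replace and record a deviation. All of this stands. It justifies the ban and shrinks the problem, but it does not give the site a compliant way to treat a severe deficit that persists.

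A reader might infer that replacement is still forbidden after infigratinib is permanently stopped. The documents do not support that. Within section 6.5.2 the herbal ban runs for the whole study and the anticancer ban for the time on study medication, while the phosphorus and calcium paragraph states no period. Section 3.2 equates trial termination with end of treatment, and section 6.4 takes a patient off study after a delay of more than 14 days. Grade 4 under the catch-all is therefore not clearly inside the gap, and the 14-day limit probably caps the ban's reach.

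A reader might also take 20% to 62% as the chance that the gap affects someone. It is the chance of any Grade 3-4 hypophosphatemia, which is a different event.

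The calcium and QTcF cases are hypothetical. X2204 reports hypercalcemia in 20.6%, the QTcF row names only potassium and magnesium deficits as electrolyte causes, and section 1.2.1.2.3 reports no QTc effect.

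**Conclusion.** The point holds within a narrow scope: a Grade 3 or symptomatic low phosphorus (after binder and diet are stopped) or low calcium, arising on treatment, in a patient on infigratinib or in a hold of up to 14 days. For that patient section 6.5.2 as written blocks replacement medication, and nothing else in the protocol lifts the block except, arguably, the QTcF row that contradicts it.

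The affected number is small and cannot be fixed from the documents. It depends on how many of roughly 0.2 to 1.0 expected Grade 3-4 cases (pooled, before sampling error) stay low, plus an unreported number of symptomatic milder ones. These figures assume that rates from other tumor types carry over to head and neck cancer. The Grade 3 or symptomatic threshold is proposed here; the protocol sets none.

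This is a patient-safety improvement worth considering. It has no effect on response rate, sample size, alpha or power.

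**What to change.** **1. In section 6.5.2, after the list of medications, add:**

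> This prohibition applies until BGJ398 is permanently discontinued. Exception: short-term replacement of a Grade 3 or worse, or symptomatic, low serum phosphorus (after sevelamer and dietary phosphate restriction are stopped) or low serum calcium arising on treatment is permitted up to the normal range. BGJ398 is held during any such replacement (or discontinued where Table 6-3 requires), and calcium and phosphorus are rechecked at least weekly and before BGJ398 is resumed.

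The hold is written into the exception because the catch-all has no hold for symptomatic Grade 1-2 deficits.

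**2. In the Grade 3 QTcF row of Table 6-3, after the electrolyte-replacement instruction, add:**

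> (including phosphorus or calcium if low, notwithstanding 6.5.2)

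A ceiling of 55 mg²/dL² on the calcium-phosphorus product is an optional safeguard. Table 6-3 uses that figure in the creatinine row ("Grade 1 and Pi >5.5 mg/dL and/or tCa x Pi >55"), as a dose-modification criterion and not as a replacement rule. Exclusion 14 stays as it is.

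**Cost.** Two short insertions at the next amendment and no extra patients. Affected patients may need a few extra chemistry checks, since scheduled chemistry falls to Day 1 only from Cycle 3. However, patients interrupted or stopped "due to an adverse event or abnormal laboratory value must be followed at least once a week for 4 weeks" under section 6.4 already. There is a small risk of overshoot: phosphorus above 7.0 mg/dL despite phosphate-lowering therapy triggers a hold, and above 10.0 mg/dL discontinuation. The hold, the normal-range limit and the rechecks contain that risk.
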